4.4 Outcomes of the Evaluation

- A refined logic model.
- An empirically informed systems' map for physical activity in Bracknell Forest.
- A narrative capturing referral and non-service user experience and engagement with the service.
- Recommendations for improvements of the BFHWBPAS going forward.
- Best practice guidance for councils aiming to employ the service model.

5. STUDY DESIGN AND SETTING

To address the complexity of the four **research** objectives, this evaluation will adopt a mixed-methods research design and comprise of three work packages operating sequentially with overlapping phases.

Work package 1 – Systems mapping

Through Actor mapping, the initial phase of this evaluation will identify the key organisations, individuals and factors influencing PA in the local area, operating across multiple levels in accordance with the Whole Systems Mapping Approach (PHE 2019 and 2021). This map will be used to explore the existing PA system and how and where this service sits within the local system. There will be an initial mapping workshop with stakeholders involved with funding, promoting and referring service users with a follow up workshop after two months. Online/Telephone interviews with the identified key stakeholders representing various roles e.g., policy makers, practitioners, service delivery managers across multiple levels of the service delivery will explore their experiences of the service design, implementation, and referral pathways. They will also review the Actor map and offer feedback for its refinement. The workshops, COVID-19 guidance permitting, will take place onsite at a location of the partner's choosing.

Work package 2 – Service evaluation from referral perspective

This work will follow a prospective approach comprising longitudinal qualitative case study interviews with BFHWBPAS participants supplemented by Everyone Active's survey data (recording reasons for service discontinuation) and a statistical analysis of service data (routine outcome data collected by the partner). The latter will allow an understanding of whether the BFHWBPAS achieves an impact in line with other researched ERS. Interviews will take place via Microsoft Teams audio/video call or telephone call, depending on participant access and preference.

Work package 3 – Service evaluation from targeted non-users' perspective

The study design is descriptive and quantitative. The approach is a cross-sectional street intercept face to face survey in the location of the target groups, advised by Everyone Active. The timing, late in the research process, allows for any type of communications affecting awareness of BFHWBPAS to diffuse across the population. To identify sample elements, participants will be screened as (1) resident in a target ward, (2) inactive as defined by IPAC score (3) >18 (4) and a non-user of the BFHWBPAS. The survey will explore awareness of BFHWBPAS and recommendations and understanding of the benefits from physical activity, knowledge of local opportunities for exercising in principle, and for engagement with the BFHWBPAS specifically. Informed consent will be obtained from participants and logged in the app to be used for data collection at the beginning of every survey.

Work package 4 – cost analysis.

A small-scale work package that will include a descriptive cost analysis of the program delivery. It is not possible to conduct a full economic evaluation given the limitations of the data collected locally and the timing of the evaluation against the service delivery. However, it is possible to undertake a rigorous assessment of the costs associated with delivering the intervention.

6. SAMPLING AND RECRUITMENT (including consent processes)

Work package 1 – Systems mapping and perspectives

Stakeholders (n<20) representing key organisations across multiple levels of the service delivery will be identified through desk-based mapping work and workshops in conjunction with the partner. Key stakeholder representatives will be purposefully selected and invited by e-mail to participate in online/telephone interviews, surveys and workshops; they will be provided with a participant information sheet and consent form. Participation will be on a voluntary basis and written consent will be sought prior to the workshop, interview and survey participation. Recorded verbal consent will also be obtained during the interview.

Work package 2 – Service evaluation from referral perspective

Purposive sampling will be used for the qualitative data component. The researchers will aim to recruit 20 participants who are 18 years of age or over, have provided consent for data to be shared with the evaluation team and have been recently referred to the service. We will follow the journey of those who are i) referred and will go on to attend the service ii) referred but will not go on to attend the service and iii) referred, do attend but later drop out. This sample size could result in up to 60 interviews in total across three time points. The literature indicates that attrition for ERS may be up to fifty percent, in which case, around 10 participants from the proposed sample would be expected to fall into group one, perhaps less when also accounting for evaluation attrition. Written or recorded verbal consent will be sought prior to participants continuing to attend the service, we will actively recruit individuals referred to the service who do not become service users.

For the quantitative data component, all enrolled participants will be included in the sample population following informed written consent which will be sought during the enrolment process by the partner. The sample population will be stratified in accordance with demographics and characteristics such as health status, ethnicity, and age. There will likely be two referral pathways, one for GPs using existing referral systems and one on the 'JOY' Application which will be used by the social prescribers and the voluntary sector. The partner has submitted a request for a permissions box to be added to both to enable details of potential participants to be shared with the evaluation team. If appropriate, the partner gatekeeper managing this system will then securely transfer this data to the appropriate researcher(s) in line with the data sharing agreement.

To compensate participants for their time, we will explore the use of a voucher incentive (approximately £15 for each 30-minute interview, £25 an hour). The proposed voucher value will be discussed amongst our PPIE representatives and the evaluation team to confirm that this is perceived as reasonable.

Work package 3 – Service evaluation from targeted non-users' perspective

The population of interest for this work package accounts for around 20% of residents in the wards identified by Everyone Active as being the most socioeconomically deprived in Bracknell Forest, but the further defining criteria (inactive non-users of the new BFHWBPAS) make them a particularly hard-to-reach group. Street intercept survey is a feasible alternative to more usual methods (Miller et al., 1997) particularly for harder to reach populations (Singh, 2020) and generates moderate to high participation (Graham et al., 2014) and completion rates when a small incentive is offered (Rotheram-Boras, 2001). The study in WP3 sets out to collect categorical variables from a single sample from a

population of known size (Omair, 2014). As such, the required sample size can be estimated using freely available open-source software such as *openepi.com*. To obtain a sample that gives a 5% margin of error and a 95% confidence interval, a total of 366 participants are required for the study.

To conduct the street intercept and reduce researcher selection bias, the following process will be followed. Each interviewer stands in the pedestrian flow and imagines a line between two fixed points over which the pedestrian traffic is passing. It is then a simple matter of attempting to intercept the *n*th pedestrian for interview. If unsuccessful, the count starts again. Successful intercepts will be informed of the purpose of the survey, and the screening questions administered. Once a qualified respondent is identified, they will be offered an incentive of £15.00 to complete the survey. On any one day at any location a team of three or four researchers will be needed to cover different available traffic flows identified in advance of the operation. It is envisaged that the data can be collected over five days.

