8. DATA ANALYSIS

Work package 1 – Systems mapping a

The initial and follow up workshops will produce a conceptual 'map' of the multiple factors that constitute the system and the cross-sectoral nature of the influences on physical activity illustrating the breadth of opportunities to influence the system. The initial map will be based on existing literature and the work of Rutter et al, (2019). Qualitative systems mapping will be used to develop the map based on feedback from the core working team and wider stakeholder groups which will be captured via graphic recording and through the process of facilitation. Interviews will be analysed using Framework Analysis.

Work package 2 – Service evaluation from referral perspective

With a view to addressing the question, "how do referrals think about the service in terms of affect, acceptability and perceived impact?", IPA will be used to explore referrals' experiences and perceptions. Data will be stored and coded using the qualitative software NVivo. No prior assumptions about the data will be made. The qualitative methodology will capture idiographic experience of service involvement, allow cross-case analysis and illustrate processes of change. It may be supplemented by descriptive statistics from the partner survey capturing reasons for service discontinuation.

For the quantitative component, data collected by the partner will be descriptively analysed e.g., service uptake by deprivation level, age, ethnicity, health status. Population data will be statistically analysed for changes in health indices e.g., blood pressure, body mass index, mental wellbeing, personal wellbeing. Health indices at baseline will be compared to those at 12 weeks, and stratified according to different individual characteristics e.g., health status at baseline, activity level at baseline, programme adherence. Descriptive and statistical analysis will be accomplished using Microsoft Excel and SPSS Statistics software packages.

Work package 3 – *Service evaluation from targeted non-users' perspective*

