The final dataset will be downloaded from the Qualtrics database into the *SPSS Statistics* software package, cleaned and analysed for main patterns and associations in the distributions of its categorical variables. Responses to open-ended questions will be recoded for quantitative analysis. There are no pre-existing hypotheses; the aim is to develop insight from the data itself, which, when aligned with prior knowledge, will lead to actionable recommendations.

Work package 4 – Cost analysis

A descriptive analysis of costs will be undertaken with a distinction between commissioned cots and actual costs. A breakdown of income generated will also be captured. Data will be analysed alongside service user patient monitoring data collected as part of work package 2 and where data allows basic cost impact assessments made. Where data quality permits the analysis team will also work with BF colleagues to explore the combination of;

- a) Resource use collected
- b) Unit cost data associated with the above

c) Any suitable and/or appropriate outcome data (such as Quality of Life, Life Expectancy or change in diastolic and/or systolic blood pressure) – where quality and completeness criteria are met.

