9. ETHICAL AND REGULATORY CONSIDERATIONS

Informed consent will be sought from all participants who wish to be interviewed or take part in workshops. Additionally, as part of the work on WP2, permission will be sought from all individuals referred to the BFHWBPAS to allow sharing of their personal data with the LSBU research team, collected as part of the BFHWBPAS. Residents from the targeted areas in Bracknell and Forest will be informed that by accepting to complete the survey as part of the WP3 work they provide an implied consent for use of their data. Participant information sheets (PIS) will be provided to inform participants of the studies' aims, methods and risks, etc. Contact details will also be provided for participants to ask questions prior to taking part. Once participants have read this, they will give written or recorded verbal consent to participate in the study and for use of the data.

Participant facing documents will undergo automated readability checks, will be based on LSBU ethics panel approved templates and approved by LSBU University Ethics Panel (UEP). We will involve our PPIE representatives in the development of these documents.

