9.2 Assessment and Management of risks

And

Table	1:	Risk	register
rubic	- .	IN SIL	register

Key risk	Likelihood	Impact on participants	Impact on project	Mitigation
WP1	Low	Some participants may find the complexity of mapping challenging	Low levels of participation will make the mapping less rich	Working with the commissioner to recruit across the system
WP2 qualitative Participant discomfort discussing personal barriers to exercise	Low/ Moderate	Some participants find space to reflect helpful and cathartic, for others this may be a source of short-term psychological distress	This could increase likelihood of evaluation attrition and ability to meet target sample size	Researchers will follow guidance on how to keep participants and themselves well- supported (Silverio et al., 2022). Participants will be debriefed, and appropriate resources will be signposted.
WP2 Quantitative Participants will not agree to share their health data with LSBU researchers	Moderate	Participants may feel intimidated to share personal health data, especially in case of failing to complete the full program and achieve good progress	Missing data and failing to reach the required sample size will impact the power of the study to formulate conclusive recommendations	Data collection will start as early as possible after the launch of the BFHWBPAS. Researchers will work closely with the Health and Well-Being coaches to ensure completeness of the data base.
WP3				
Permissions to intercept in BF settings No appropriate public venues for interviews	Low / Moderate	N/A Participants may not feel relaxed enough to elaborate on their personal experiences and perspectives	Not reaching the target quota for the sampled population Lack of sufficiently rich evidence to fill in the targeted gaps in knowledge	LSBU research team will work closely with engaged local stakeholders to secure the permissions in advance. The potential venues for the street interception and the follow-up interviews will be chosen based on advice will be sought from the local collaborators and the PPIE representatives
COVID-19 interferes with staff availability (research team and stakeholders)	Moderate	N/A	Moderate	Clear project planning to facilitate handover, lines of alternative communication established, agreement to support the evaluation through a Data Sharing Agreement

				between LSBU and BF

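### The WP2 quantitative sample is enrolled, consenting users, so it has no denominator for the planned description of service uptake by deprivation, age, ethnicity and health status

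*Protocol*

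**What the plan says.** Four places in the protocol bear on who is counted.

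- **Section 6, work package 2.** The quantitative sample is fixed by enrolment and consent: "all enrolled participants will be included in the sample population following informed written consent". The partner obtains this consent at enrolment.
- **Section 6, same part.** Two referral pathways are expected, one for GPs and one through the JOY application for social prescribers and the voluntary sector. On these: "The partner has submitted a request for a permissions box to be added to both to enable details of potential participants to be shared". Transfer by the partner's gatekeeper then follows if judged appropriate.
- **Section 8, work package 2.** The data collected by the partner will be described, with "service uptake by deprivation level, age, ethnicity, health status" as the example. No numerator or denominator is given.
- **Section 9.** A wider group is named: "permission will be sought from all individuals referred to the BFHWBPAS to allow sharing of their personal data with the LSBU research team".

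Two further points matter. Section 1.2 lists self-referral as a way into the service. Table 1 in section 9.2 includes the risk "Participants will not agree to share their health data with LSBU researchers", rates it Moderate, and links reluctance to not completing the programme or not making good progress.

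**The concern.** Uptake answers the question: of those who could have started, how many did? Someone who was referred and never enrolled is a failure of uptake, and the section 6 definition leaves that person out. A table of enrollees by deprivation shows who is in the service. It cannot separate a group that was seldom referred from a group that was often referred but seldom started, or from a group that started but did not agree to share data. These three call for different action by the service.

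This matters because reducing inequalities is in the study title and is one of the knowledge gaps in section 2, and section 4.2 asks how the service's characteristics influence uptake. The other components do not fill the gap. The 20 interviewees in work package 2 are chosen purposively, and work package 3 surveys only non-users, so neither can estimate uptake.

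A later analysis plan could define uptake, but it could not recover counts that were never requested. What the partner supplies is settled by the protocol, the consent wording and the data sharing agreement.

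**Working it through.** The protocol gives no referral, enrolment or consent numbers for this component, so there is no stated figure to reproduce. The check is one of logic. The numbers below are assumed, show the mechanism only, and are not estimates of size.

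**Step 1. What the section 6 sample contains.** For stratum *s*, let R be the number referred, u the proportion who enrol, and c the proportion of enrollees who consent. The number in the dataset is

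n = R × u × c.

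Only n is observed. The target is u. Everyone in the dataset has enrolled, so enrolled divided by sample size is 100% in every stratum by construction.

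**Step 2. Counts of enrollees do not determine uptake.** Set consent aside (c = 1) and suppose 30 enrollees from the most deprived stratum and 20 from the least deprived.

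| Referred, most / least deprived | Uptake, most deprived | Uptake, least deprived |
|---|---|---|
| 60 / 40 | 30/60 = 50% | 20/40 = 50% |
| 120 / 40 | 30/120 = 25% | 20/40 = 50% |
| 60 / 80 | 30/60 = 50% | 20/80 = 25% |

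The same dataset fits equal uptake, lower uptake among the deprived and higher uptake among the deprived. This holds even with full consent, so it does not depend on any assumption about refusals.

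**Step 3. Does the referral-stage permission supply the denominator?** Suppose section 9 were applied to this analysis, so that numerator and denominator both come from referred people who agree to share data. With cA and cN the agreement rates of attenders and non-attenders,

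observed uptake = u × cA / [u × cA + (1 − u) × cN].

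Take u = 50% and cA = 0.8 (both assumed):

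- cN = 0.8: 0.40 / (0.40 + 0.40) = 50%, no distortion
- cN = 0.6: 0.40 / (0.40 + 0.30) = 57%
- cN = 0.4: 0.40 / (0.40 + 0.20) = 67%

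If non-attenders agreed more readily than attenders, the error would run the other way. If agreement differed by deprivation but not by attendance, it would cancel within each stratum.

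**Step 4. Coverage of that route.** The box has been requested, not confirmed. It is described for the GP and JOY pathways, and self-referral is not mentioned among them. Its stated purpose is to pass on details of potential participants, and nothing connects it with the uptake table. Section 9.1 also requires service users' permission before their data are shared. No aggregate count of all referrals is mentioned anywhere.

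**The case against.** The best reply is that sections 6 and 9 describe two steps: permission at referral, then written consent at enrolment. On that reading they need not contradict each other. Section 8 also ties uptake to data collected by the partner and does not say that the enrolled sample is the only source. Uptake by deprivation appears there only as an example of a descriptive breakdown, and section 7 calls the quantitative data a supplement to the interviews. The exact definition of a descriptive variable is often left to an analysis plan.

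Part of this stands. A reader might infer that the protocol offers no route at all to data on referred people. That goes too far, because section 9 and the permissions box describe one. The supportable point is that the route is not assigned to this analysis and is incomplete. A reader might also take uptake by deprivation to be the study's designated measure of inequality. The protocol does not give it that status, although the title and rationale make it an obvious result to look for.

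What the reply does not supply is a denominator. Read as two steps, the text still leaves the only defined quantitative sample at enrolled consenters.

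**Conclusion.** The point holds as a gap in the definition of the analysis population. Section 6 defines a sample from which the uptake described in section 8 cannot be computed, and section 9 names a wider population without linking it to that analysis. As written, the output would be the composition of consenting enrollees. This conclusion needs no assumed rate. It rests on reading uptake as a proportion of people referred. If uptake per resident were meant, the denominator would have to come from outside the dataset, the protocol does not say so, and consent would still affect the numerator.

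Distortion by selective consent is a risk and not a demonstrated bias. It requires consent to differ between groups, or between attenders and non-attenders. The protocol rates refusal as Moderate and expects it to be related to completion, and the mitigation (an early start and work with the coaches on completeness) does not address selectivity. With no consent rates in the document, the size and direction cannot be stated.

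A reader might infer that work package 4 would overstate costs per user, since section 8 says "Data will be analysed alongside service user patient monitoring data collected as part of work package 2". The documents do not support this: they plan a descriptive cost analysis, and no cost per consented user is specified.

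**What to change.** 1. Define uptake in section 8 as the number who started divided by the number referred, in each stratum.
2. Ask the partner for anonymous aggregate counts of all referrals and all starters, by referral route (GP, JOY, self-referral), cross-tabulated by deprivation and by any other of the listed characteristics that are recorded at referral. Use these counts for uptake, so that neither numerator nor denominator depends on individual consent.
3. Keep the consented individual records for the comparison of baseline with 12 weeks. Tabulate consenters against all starters on the same characteristics, so that selection by consent can be seen.
4. Reconcile sections 6, 8 and 9 by stating which population feeds which analysis, and state in the data sharing agreement that the aggregate counts are included.

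The cost is one extra aggregate request under the planned data sharing agreement, which could accompany the access to partner data scheduled for August 2023 in Table 2, plus changes of wording. No further participants are needed. The limit is what the partner records for people who never enrolled. Where ethnicity or health status is not held for them, uptake should be reported only for the characteristics that are, and the rest described as the mix of enrollees.
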